15.3 Notification of SAEs via GP

Once a participant is recruited to the study, the participant's GP will be notified by letter. The notification letter includes a request for the GP to contact the CTU in the event of the GP becoming aware of any SAE. On being informed of an SAE, the CTU will liaise with the relevant local RA who will be responsible for ascertaining further details about the SAE from the participant and/or GP records as appropriate.

15.4 Notification of SAEs from other sources

It is possible that the local research team or CTU may become aware of an SAE via patient or relative self-report or some other channel. In such cases, the local RA will be informed of the SAE in order to ascertain further details for reporting to the CTU.

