7.1 Trial schema

7.2 Study personnel

The study will be led at each of the four collaborating University sites (Plymouth University, Nottingham University, St George's University of London, and Oxford University) by a local Principal Investigator.

All study personnel undertaking home visits will be asked to comply with their employers' lone working policy. All staff working with study participants will be required to complete Disclosure and Barring Service (DBS) checks, as they may be working with vulnerable individuals.

Health trainers will be part of the research team and trained to support participants in the intervention. They will be line managed by the site PI and receive training and supervision by a member of the lead site research team.

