9 INTERVENTION

9.1 TARS Intervention

Participants in the intervention arm will be offered open-ended support from a Health Trainer (HT) which will broadly include the content described in Table 1 below. In the interests of ensuring it meets the participants needs the HT will suggest options for the support provided but empower the participant to decide what support is offered, where and when. In the pilot EARS trial participants had an average 4.2 sessions by phone or face to face with the HT with a range of 0-8 [1]. If a smoker wishes to quit at any time during the 8 week intervention period, they will be offered 6 weeks of additional behavioural and motivational support from the HT, as well as support to access services as part of usual care to stop smoking (as available at each location) if desired. If a smoker wishes to reduce smoking using e-cigarettes or licenced nicotine containing products (LNCP) they will also be offered any local available support for this. Typically, there are no formal programmes for use of medication during reduction and people usually buy their own NRT or, more often, e-cigarette or vaper product. We will also monitor any national guidelines (eg, NICE PH45 guidelines for smoking harm reduction) for any changes and adopt our actions and guidance accordingly throughout the trial.

The goal of the intervention is to promote motivation to make a quit attempt. If a smoker wishes to quit at any time during the 8 week intervention period, they will be recommended to attend a stop

smoking service, where they will be offered and pharmacological and behavioural support that comprises usual smoking cessation practice. If the participant prefers, the health trainer could continue to provide cessation support and recommend options for use of pharmacotherapy.

Intervention components	Aim	Content	Process and outcome evaluation
Active participant involvement (1)	Develop rapport, build trust, and shared respect.	Effective communication skills. Build autonomous support.	Participant feedback on HT-led support.

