14.2 Protection against risks

During the screening process those smokers who are contraindicated for moderate intensity physical activity, or who have injury or illness which might be aggravated by exercise, will be required to gain approval from their GP before engaging in the study. Vigorous intensity activity can acutely and transiently increase the risk of sudden cardiac death and acute myocardial infarction in susceptible persons, so the focus of all recommendations for increasing PA will be on moderate intensity PA. Participants will be given clear guidance on exercising at this intensity (ie, something that increases the heart and breathing rate but not to the point of breathlessness or unable to maintain a conversation). Participants will be advised to seek approval from their GP prior to engaging in any vigorous intensity PA, regardless of age and gender. The smokers will be monitored for contraindications to exercise, for adverse events including physical symptoms (e.g. chest pain, extreme breathlessness), or change in health status at each counselling session.

All study personnel will be asked to comply with their employers lone working policy. All staff working with study participants will be required to complete Disclosure and Barring Service (DBS) checks, as they may be working with vulnerable individuals.

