15.1.3 Reporting requirements for this study

The recording and reporting of non-serious AEs in this study is not required. SAEs will be reported from the time of consent until 4 months after the last trial intervention. If an unreported event from this time period is identified at a later date, retrospective reporting must occur immediately. Events occurring outside of this time period may still be reported if the Investigator feels that it is medically important. Information about SAEs may be captured in a variety of ways (see below). SAE report forms will be returned to the CTU, and entered into the study database. The Trial Office is responsible for reporting relevant events to the Sponsor, and ethics committee within required timelines in accordance with trial procedures and regulatory requirements. The PI is responsible for reporting events to local parties, in accordance with local practice. All reportable events and any others as advised by the main REC, will be sent to Investigators for submission to relevant parties in accordance with local practice. Trial staff will send a safety report to the main REC, and to the Sponsor annually. Sites should distribute this report in accordance with local practice and regulatory requirements.

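### Serious adverse events have an extra way of coming to light in the intervention arm only, and the protocol does not require the notification route to be recorded so that an imbalance could be interpreted

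*Protocol*

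**What the plan says.** Protocol section 15 describes three ways in which an SAE can reach the CTU.

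- **Booklets (15.2).** Participants in both arms are asked about hospital admissions at 3 and 9 months, with recall of three and six months respectively.
- **GP (15.3).** The GP of every recruited participant is asked by letter to report SAEs.
- **Anything else (15.4).** "It is possible that the local research team or CTU may become aware of an SAE via patient or relative self-report or some other channel".

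Under 15.1.3, SAE forms from any route go to the CTU and into the study database. Non-serious events are not recorded. Section 15 does not ask for the notification route.

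Three other sections bear on the third route. Section 14.2 says that smokers will be monitored "for adverse events including physical symptoms (e.g. chest pain, extreme breathlessness), or change in health status at each counselling session". Under section 9.1 these sessions belong to the intervention arm, and "In the pilot EARS trial participants had an average 4.2 sessions by phone or face to face with the HT", with a range of 0 to 8. Section 7.2 states that "Health trainers will be part of the research team". Section 9.2 gives both arms written or web guidance and describes no periodic enquiry for controls.

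Section 10.4 expects 60-65% to complete 3-month follow-up. Section 20.5 has the data monitoring committee (DMC) review safety data and advise on amending or terminating the trial, on safety among other grounds.

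**The concern.** An admission in the first weeks after randomisation can surface in either arm through the booklet or the GP. In the intervention arm it can also surface at a session with a member of the research team whose task includes watching for changes in health. If the 3-month booklet is not returned, the 9-month booklet does not repair the gap, because its six-month recall starts at about month 3. The booklet asks about hospital admission, so other SAEs depend on the GP or on section 15.4.

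A count by arm therefore mixes true incidence with intensity of observation, and the mixture leans against the intervention. If the DMC saw more SAEs in that arm, it could not tell harm from better detection. The route is a data-collection item. If it is not captured when the event is reported, no later analysis plan can reliably rebuild it.

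**Working it through.** The protocol states no SAE rate, expected count or between-arm SAE test, so it has no figure to reproduce. The calculation below is an illustration.

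**From the protocol:** booklet response r = 0.60 to 0.65 (10.4); intervention period 8 weeks (9.1); 450 per arm (section 4); booklets to 9 months, taken as 39 weeks.

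**Assumed:** equal true risk and equal r in both arms; an admission is captured by the booklet with probability r; g = probability that the GP reports an event; h = probability that an event otherwise missed surfaces at a trainer session; routes independent.

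**Formulas.** Proportion of true SAEs detected:

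- control: D_C = 1 − (1 − r)(1 − g)
- intervention: D_I = 1 − (1 − r)(1 − g)(1 − h)

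The expected ratio of recorded SAEs with no true difference is D_I / D_C.

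**Months 0-3, with trainer capture applied to the whole period:**

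| r | g | h | D_C | D_I | Ratio |
|---|---|---|---|---|---|
| 0.65 | 0 | 0.40 | 0.65 | 0.65 + 0.35 × 0.40 = 0.79 | 1.22 |
| 0.60 | 0 | 0.80 | 0.60 | 0.60 + 0.40 × 0.80 = 0.92 | 1.53 |
| 0.65 | 0.5 | 0.40 | 0.825 | 0.895 | 1.08 |
| 0.60 | 0.5 | 0.80 | 0.80 | 0.96 | 1.20 |
| 0.60 | 0.3 | 0.25 | 0.72 | 0.79 | 1.10 |
| any | 1 | any | 1 | 1 | 1.00 |

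The algebraic limit (g = 0, h = 1) is 1/0.60 = 1.67 or 1/0.65 = 1.54. It requires that trainers hear of every event the booklet misses and that GPs report none.

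**Over 9 months.** Take events as uniform in time, the same booklet capture throughout, no GP reports, and trainer contact in 8 of 39 weeks (fraction 0.205). The ratio is 1 + (1 − r) × h × 0.205 / r.

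- r = 0.65, h = 0.40: 1 + 0.14 × 0.205 / 0.65 = 1.04
- r = 0.60, h = 0.80: 1 + 0.32 × 0.205 / 0.60 = 1.11

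The six further weeks of support offered to those who wish to quit (9.1) would raise these somewhat. So would a reporting period that ends before 9 months.

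**What this does to counts.** Assume a true risk of 5% in both arms, which gives 450 × 0.05 = 22.5 true events per arm.

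- No trainer route (r = 0.60, g = 0): 13.5 v 13.5. The chance that the intervention count is higher is 46%, and the chance of a nominally significant intervention excess is 2.5%.
- r = 0.60, g = 0, h = 0.5: 13.5 v 18.0, ratio 1.33. The chances are 77% and 13%.
- r = 0.60, g = 0.3, h = 0.25: 16.2 v 17.8, ratio 1.10. The chances are 57% and 5%.

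**Booklet and GP routes only.** Here h drops out and the expected ratio is 1.00, provided r and g are the same in both arms.

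**The case against.** A reader might infer that SAEs are actively sought at sessions, that all routes will be pooled, and that an intervention excess will therefore appear even if none exists. The documents do not support that.

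- Section 14.2 concerns exercise safety. It speaks of adverse events, symptoms and health status, and does not make the session an SAE-collection point. Section 15.4 is passive and neutral as to arm.
- The protocol states no between-arm SAE comparison and no pooling rule. Tabulation may be settled in the SAP, which is not shown, and the SAE form may already have a source field.
- The two structured routes cover both arms. Trainer contact is concentrated in 8 weeks, and some pilot participants had no sessions. Booklet non-responders may also be those with few sessions, and lower booklet return in the intervention arm could offset the bias.
- Ratios of 1.2 to 1.5 require that GPs recover nothing the booklet missed and that trainer capture covers all of months 0-3. The 40-80% trainer capture has no source.

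All of this stands, and it limits the point to a tendency of unknown size. It does not remove the asymmetry, because trainers are in the research team and what they learn has an open way into the SAE record.

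A second objection concerns the remedy. Comparing the arms on booklet and GP reports alone would discard known events. Someone who dies cannot return a booklet, so a death reported by a relative could drop out. Harm from promoted exercise is what trainers are best placed to hear of. This is right, and the fix below keeps every event in the main comparison.

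**Conclusion.** The point holds as a moderate weakness in how safety data are collected. Ascertainment is unequal between the arms, and the expected direction is towards more recorded SAEs with the intervention. The ratio could be 1.00 if GPs report every event. It could reach about 1.5 for months 0-3 if they report none and trainers hear of most events the booklet misses. Over 9 months, with no GP reports and trainer contact limited to 8 weeks, it is roughly 1.04-1.11. These figures rest on assumed capture probabilities, equal true risk, equal booklet return and independent routes. Only the 60-65% response, the 8 weeks and the arm sizes come from the protocol. An observed excess is not certain, and the primary outcome and the power are unaffected.

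**What to change.** In section 15.1.3, require the CTU to record for every SAE the route of first notification (booklet, GP, health trainer, other) and any later confirmation by booklet or GP. The CTU should hold this field and keep it from site researchers, because a trainer route reveals the allocation that section 8.8 tries to conceal from them.

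Keep the table of all SAEs by arm, including all deaths, as the main safety table for the DMC and the final report. Add beside it a supporting table of events captured by the routes common to both arms (booklets and GP). An event first heard of from a trainer and later confirmed by booklet or GP counts in both. Show booklet return by arm with it, since the supporting table is balanced only if return is similar.

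The cost is one extra entry on the form and one extra table. No known event leaves the comparison, and SAE reporting is otherwise unchanged.

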15.5 Death/life threatening events

In the case of death or life-threatening events, on the day of becoming aware of the event, please telephone the Trial Office. The appropriate CRFs must be submitted in accordance with the CRF schedule. In the case of death, where possible, a copy of the death certificate and post-mortem report (if applicable) should be submitted to the Trial Office as soon as possible. Names and hospital numbers must not be visible on these documents. The participants trial number and initials must be clearly added to the document using black ball-point ink.

16 DATA MANAGEMENT

16.1 Data collection

Data will be recorded on study specific data collection forms (CRFs), by a suitably qualified individual cited on the site signature and delegation log. Participants will complete participant-reported outcome measures (PROMs). Data will be collected on paper for both study arms. All persons authorised to collect and record study data at each site will be listed on the study site delegation logs, signed by the relevant PI. Original versions of the CRF should be sent to CTU, and copies kept at site.

Trial staff will maintain regular communication with sites, through routine calls, mailings and/or meetings. In the event of persistent issues with the quality and/or quantity of data submitted, an on-site monitoring visit may be arranged. In such circumstances, patient notes and the investigator site file must be available during the visit. The representative from the Trial Office will work with the site staff to resolve issues, offer appropriate training if necessary, and determine the site's future

participation in the trial. An audit may be arranged at a site if the Trial Management Group feels it is appropriate. Audits will be conducted by an independent team, determined by the Trial Management Group. If a regulatory inspection is planned at a participating site, site staff should contact the Trial Office to discuss any action necessary.

16.2 Participant numbering

Each participant will be allocated a unique study number following randomisation, and will be identified in all study-related documentation by their study number and initials. A record of names, addresses, telephone numbers and email addresses linked to participants' study numbers will be stored securely on the study database for administrative purposes.

16.3 Source data

For the purposes of this study source data will include:

- 1. Patient's medical records, held by the NHS.
- 2. Patient self-reported outcome measures (PROMS) completed in the questionnaires at baseline, and the 3, 9 and 15 month follow-up assessments. Accessible by members of the CTU.

Source data will be made available for the purposes of on-site monitoring visits, audits, and regulatory inspections.

16.4 CRF completion

Each site will be provided with an Investigator Site File (ISF) containing Case Report Forms (CRFs). Data collected on each participant must be recorded by the local Principal Investigator, or designee, as accurately and completely as possible. The Principal Investigator is responsible for the timing, completeness, legibility, accuracy and signing of the CRFs, and he/she will retain a copy of each completed form. All fields MUST be completed. If a test or measurement was not done, please indicate why that was omitted on the CRF. Entries must be made in black ballpoint pen. Errors must be crossed out with a single line leaving the original data un-obscured (i.e. without overwriting), the correction inserted and the change initialled and dated. An explanatory note should be added if necessary. Correction fluid/tape/labels must not be used. All data submitted on CRFs must be verifiable in the source documentation. Any deviation from this must be explained appropriately.

Completed CRFs should be returned to:
TARS Study Office
Peninsula Clinical Trials Unit
Plymouth University Peninsula Schools of Medicine & Dentistry
[name]
[name]
Plymouth
[name]

TARS Protocol Version 2 26OCT2017

16.5 Questionnaires

In order to determine if the intervention has an effect on reducing smoking, participants will be asked to complete a questionnaire booklet, at baseline, 3 months, 9 months and 15 months (if applicable). The baseline questionnaire booklet should be given to, or posted to participants after written consent is obtained but prior to study randomisation. Further questionnaire booklets will be posted to participants at the 3, 9 and 15 (if applicable) month time points. Completed questionnaire booklets should be returned to the CTU using the pre-paid envelopes provided.

16.6 Data handling and record keeping

Completed CRFs will be checked and signed at the collaborating University sites by a suitably qualified member of the research team before being sent to the CTU. Original CRF pages and questionnaires will be posted to the CTU at agreed timepoints with copies of the CRF retained at the relevant study site. Forms will be tracked using a web-based study management system. All data will be double-entered by the CTU on to a password-protected database. Double-entered data will be compared for discrepancies using a stored procedure and discrepant data will be verified using the original paper data sheets. Incomplete, incoherent, unreadable or other problem data in the CRF pages will be queried by the CTU with study site staff during data entry to ensure a complete and valid dataset. Questionnaire data will not be queried with participants. The CTU may complete further validation of data items, perform logical data checks and raise further data queries after data collection has been completed. The final export of anonymous data will be transferred to statisticians for analysis after all data cleaning duties have been performed by the CTU, this will usually be via email or a removable storage device. Identifiable information will not be exported from the study database as part of the final export.

Accelerometers will be received by the CTU and data will be downloaded and linked to participant ID numbers. Files will be checked before the accelerometers are recirculated. Files will be then further analysed with bespoke software to classify data into levels of physical activity intensity using accepted cut-points. Standard operating procedures will be applied to make a decision about dealing with missing data. Selected primary and secondary accelerometer derived outcomes will be merged into an individual participant data set, and securely stored as below.

Identifiable information will be omitted from the transcriptions of the process evaluation interviews.

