7.4 Primary outcome

Carbon monoxide (CO) verified prolonged abstinence over 6 months

We will use guidance provided by Aveyard *et al* (2009) [75] on floating prolonged abstinence. Study participants who report abstinence on the 3 month mailed survey (which is confirmed by face to face CO expired air assessment) and then again self-report abstinence (and not having smoked even a puff since the 3 month assessment) on the 9 month mailed survey (which is again confirmed by CO expired air assessment), will be identified as having prolonged abstinence over at least 6 months.

The CO monitor used in this study is a Bedfont Micro CO monitor. The CO measurement involves the participant holding their breath for 10-15 seconds, and then blowing into the monitor. The carbon monoxide value in parts per million (ppm) is shown with values below 10 ppm indicating abstinence. The reading at each recruitment site will be reported remotely into the on-line PenCTU data management system. The CO monitor will be regularly calibrated to ensure accurate measures.

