7.5 Secondary outcomes

Point prevalence CO verified abstinence at 3, 9 and 15 months post baseline

Only those reporting abstinence by mailed survey at 3 and 9 months will be contacted for CO verification. Only those abstinent at 9 months will be followed up at 15 months by mailed questionnaires and if abstinent by face-to-face assessment of expired CO.

Self-reported smoking and use of aids to reduce/quit smoking

Study participants will be asked to self-report the number of cigarettes smoked and type of nicotine product, i.e. pipes, cigars and roll your own. The same formula used in the EARS pilot study will be used to convert amount of loose tobacco into number of cigarettes [1].

Questions to capture use of e-cigarettes and NRT (nicotine replacement therapy) products

Physical activity

Questions at baseline, 3 and 9 months will assess self-reported 7-day physical activity recall. A sub set of all participants in the TARS study will be invited to wear an accelerometer for a 7 day period during the study. The accelerometer, and instructions for use will be mailed to selected participants at the 3 month time point from CTU, along with the 3 month questionnaire booklet. The accelerometer is waterproof, and is worn continuously for 7 days. At the end of the 7 days the participant should return the accelerometer to the CTU in the freepost envelope provided.

Self-reported height and weight - Body Mass Index (BMI)

At baseline, 3 and 9 months participants will be asked to self-report their height and weight. The questions will be part of the questionnaire booklet mailed to participants from CTU at baseline, 3 and 9 months. Based on the weight and height reported we will derive a measure of BMI.

Health related quality of life (EQ-5D-5L & SF-12)

EQ-5D-5L

This is described in section 19.1.

SF-12

The SF-12 is a 12-item, patient-reported survey of patient health, consisting of twelve questions [70]. In this study participants will be asked to complete the SF12 as part of the questionnaire booklet mailed to them from CTU at baseline, and then at 3 months follow-up and 9 months follow-up.

Health economic outcomes

Health service utilisation and costs, including smoking related costs

Process measures

The following process measures will also be assessed as part of the self-report questionnaire booklets issued to all participants by CTU at the baseline and 3 months:

- Importance and confidence in smoking reduction and cessation

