13 COMPLIANCE

Appointments will be arranged at times and places to suit the participant. Up to two reminder letters, and a follow-up phone call will be made to participants if they don't return the accelerometer. Up to two reminder letters will be issued to remind participants to return the questionnaire booklets, and the option of the participant telephoning a member of the research team to aid completion of the questionnaire booklets will be offered. A shopping voucher will be mailed to participants upon CTU receipt of the completed baseline, 3, 9 and 15 month questionnaire booklets. Motivational postcards may be mailed to participants ahead of the 3, 9 and 15 month follow-up assessments being sent out to increase response rates.

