17 STATISTICAL CONSIDERATIONS

17.1 Sample Size

Since the primary analysis is a comparison in each allocated group of the proportions of the primary binary outcome, the sample size is calculated for a two-sided Fisher exact test. An abstinence rate of 5% for the control group, and detectable effect of 6% (i.e.: an increase from 5% to 11% due to the intervention) are conservative estimates consistent with those from the EARS pilot study and those reported from a systematic review of pharmacological interventions. The corresponding odds ratio for this effect is 2.35. Participants with missing outcome data will be assumed to be still smoking, and the number of participants in each allocated group are assumed to be in the ratio of 1:1. Under these conditions, according to Stata v14.2, the minimum number of participants required to detect an abstinence rate of 11% compared to that of 5% in the control group with a significance level of no more than 5% and power of at least 90% is exactly 900, above which a power in excess of 90% is maintained (Figure 1). The Stata code and the R code used to verify this calculation is found in Appendix 2.

TARS Protocol Version 2 26OCT2017

[figure not shown]

Figure 1: Plot of power of test afforded by each sample size ranging from 884 to 916, for equal group sizes and 5% significance level, where the proportion of CO-confirmed abstinence rates at 9 months is 0.05 and 0.11 in the control and intervention group, respectively.

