17.2.2 Primary analysis of primary outcome

The primary analysis will be a logistic comparison of the primary outcome of CO-confirmed abstinence at 3 and 9 months post-baseline, using a mixed-effects model to account for clustering by site, with the adjustment for the HSI stratification factor, as well as important baseline covariates (i.e. age, gender, socio-economic status, level of smoking, recent quit attempts. Interpretation of the

TARS Protocol Version 2 26OCT2017

primary effectiveness will be based on the adjusted odds ratio from this model, and the point estimates reported with 95% confidence intervals. Those participants with missing outcome data will be assumed to be still smoking [6].

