
20 DATA MONITORING

The CTU trial manager and data manager will devise a risk-based monitoring plan specific to the study which will include both central monitoring strategies and study site visits (usually by the trial manager) as appropriate. The monitoring plan will be agreed by the Sponsor and PMG and reviewed periodically in line with updated risk assessments. The risk assessment and monitoring plan are active documents and will remain subject to change throughout the study.

Data will be monitored centrally for quality and completeness by the CTU and every effort will be made to recover data from incomplete pages. The CTU data manager will oversee data entry and initiate processes to resolve data queries where necessary.

All study procedures will be conducted in compliance with the protocol and according to the principles of Good Clinical Practice (GCP). Procedures specifically undertaken by the CTU team (e.g. data management, trial management and study monitoring) will be conducted in accordance with CTU SOPs. The PIs and the participating NHS Trusts will be required to permit the CTU trial manager or deputy to undertake study - related monitoring to ensure compliance with the approved study protocol and applicable SOPs, providing direct access to source data and documents as requested.

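### Section 16.6 bars querying questionnaire data with participants and makes no exception for the smoking-status answers that alone trigger CO verification

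*Protocol*

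**What the plan says.** **Data handling.** Protocol section 16.6 treats two kinds of form differently. For case report forms, "problem data in the CRF pages will be queried by the CTU with study site staff during data entry". For booklets, "Questionnaire data will not be queried with participants". No item is exempted from the second rule. Section 20 adds that "every effort will be made to recover data from incomplete pages", without saying whether questionnaire pages are meant.

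**Route to the primary outcome.** Section 7.5 states: "Only those reporting abstinence by mailed survey at 3 and 9 months will be contacted for CO verification". Sections 10.1 and 10.2 repeat that trigger for the two visits. Section 7.4 requires a CO-confirmed report of abstinence at 3 months and again at 9 months.

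**Missing data.** Section 17.2.2 states: "Those participants with missing outcome data will be assumed to be still smoking".

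**Safeguards.** Section 13 provides for booklets that do not come back: "Up to two reminder letters will be issued to remind participants to return the questionnaire booklets", with the option of completing the booklet by telephone. It does not mention a booklet that comes back with an unusable answer.

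**The concern.** The smoking-status answer does two jobs. It is a data item, and it is also the gate to the biochemical test. A no-query rule is ordinary for most questionnaire items, where a blank costs one value in a secondary analysis. Here a blank, unclear or contradictory answer can cost the primary outcome of someone who did respond.

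The loss cannot be repaired later. Under section 7.4 a missed 3-month verification is not replaced by anything at 9 months. A missed 9-month verification also removes the person from the 15-month follow-up, which section 10.3 restricts to those confirmed as quitters at 9 months. Whether that follow-up takes place at all depends on p<0.05 for the same outcome (section 17.2.5).

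If such losses were equal in both arms, both abstinence rates would fall and power with them. If they differed by arm, the estimated odds ratio would be biased. Participants know their allocation (section 8.8), so equality cannot be taken for granted, although nothing in the protocol shows a difference.

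**Working it through.** **Step 1: follow one booklet through the text.** Suppose an abstinent participant returns the 3-month booklet and smoking status cannot be read from it.

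1. The booklet has been returned, so the reminders in section 13 do not apply. The telephone option is a way to complete the booklet, offered before its return.
2. Section 16.6 rules out querying the participant.
3. There is no report of abstinence, so sections 7.5 and 10.1 produce no CO invitation. The face-to-face visit asks about prolonged abstinence again, but only people who have been invited attend it.
4. The 3-month confirmation required by section 7.4 is absent, and section 17.2.2 scores the participant as smoking.

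The same chain applies at 9 months.

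**Step 2: reproduce the planned sample size.** The inputs from section 17.1 are "an increase from 5% to 11% due to the intervention", a two-sided Fisher exact test at 5%, 1:1 allocation and power of at least 90%. Enumerating the two binomial distributions exactly gives power 0.8995 at N = 898 and 0.9003 at N = 900, and power stays above 0.90 up to N = 916. The stated 900 is reproduced. The odds ratio is (0.11/0.89)/(0.05/0.95) = 2.348, against 2.35 stated. Expected successes are 450 × 0.05 = 22.5 and 450 × 0.11 = 49.5, or 72 in total.

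**Step 3: illustrate the size.** The protocol gives no rate of unusable smoking answers. Let q be the assumed share of abstainers affected at each wave, independent between waves and equal in both arms. The share of successes retained is k = (1 − q)². The observed rates are 0.05k and 0.11k, and the successes lost are 22.5(1 − k) and 49.5(1 − k). This treats 5% and 11% as rates before any such loss.

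| q per wave | k | Control rate | Intervention rate | Lost, control / intervention | Odds ratio | Fisher power, N = 900 |
|---|---|---|---|---|---|---|
| 0 | 1 | 5.00% | 11.00% | 0 / 0 | 2.348 | 0.900 |
| 1% | 0.9801 | 4.90% | 10.78% | 0.45 / 0.99 | 2.345 | 0.893 |
| 2% | 0.9604 | 4.80% | 10.56% | 0.89 / 1.96 | 2.342 | 0.886 |
| 5% | 0.9025 | 4.51% | 9.93% | 2.19 / 4.83 | 2.332 | 0.863 |
| 10% | 0.81 | 4.05% | 8.91% | 4.27 / 9.40 | 2.317 | 0.818 |

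**Step 4: unequal loss.** With q = 5% in the intervention arm only, the rates are 5.00% and 9.93%, the odds ratio is 2.09 and power is 0.77. With q = 5% in the control arm only, they are 4.51% and 11.00%, the odds ratio is 2.62 and power is 0.95. These two cases show the direction of bias. They are not forecasts.

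**The case against.** Several points on the other side stand.

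- **A contradiction between sections 16.6 and 20.** A reader might infer that one section forbids what the other promises. The text does not establish this. Section 16.6 uses the word pages for CRF pages, so the recovery promise in section 20 can be read as covering those alone. The wording is ambiguous and should be settled. The gap also does not arise from any conflict: it comes from the no-query rule, the self-report trigger and the missing-data rule together. If section 20 did cover booklets, the participant could be recovered.
- **Certain loss from one blank item.** A reader might infer that any blank removes a success. The booklet is not shown. It covers smoking behaviour as a topic, and section 7.5 says cigarette numbers are also asked, so one blank may leave abstinence readable. Telephone completion should reduce blanks at source. The point is limited to booklets from which status cannot be determined.
- **Other contact is allowed.** Section 15.2 has the CTU ask the local research assistant for details, from the participant or GP records, when a booklet reports a hospital admission. This suggests that the rule in 16.6 was aimed at routine data cleaning. It also shows that an exception was written for admissions and none for smoking status.
- **The planning rates may already be net.** Section 17.1 lists missing counted as smoking among the conditions of the calculation. If 5% and 11% are read that way, planned power is unaffected.
- **Scale.** Section 10.4 expects only 60–65% to complete the 3-month follow-up. Unusable answers are likely to be minor beside non-return.
- **Convention and procedures.** Counting missing as smoking is a deliberate, referenced convention and is not challenged here. Working procedures may also deal with blanks, but they would have to depart from an unqualified sentence in the protocol.

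**Conclusion.** The point holds as a gap in a stated rule. Read together, sections 16.6, 7.4, 7.5 and 17.2.2 allow a participant who responded, and who may be abstinent, to be scored a smoker without being offered a CO test, and no other section closes that route.

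The size is unknown and probably small. For an assumed 1% to 5% per wave, equal in both arms and with planning rates not already net of missing outcomes, about 1 to 7 of the 72 expected successes are lost (0.45 + 0.99 = 1.44; 2.19 + 4.83 = 7.02). Power falls from 0.90 to between 0.89 and 0.86. The odds ratio, on which section 17.2.2 bases interpretation, barely moves. It would be biased only if the losses differed by arm, for which the protocol offers no evidence.

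These figures do not support a claim that the trial is underpowered. The change is worth making because it is cheap and the loss cannot be recovered afterwards.

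**What to change.** 1. **Section 16.6.** Add one exception. When smoking status or abstinence in a returned 3-, 9- or 15-month booklet is blank, unclear or contradictory, the CTU asks an allocation-blind local researcher to telephone the participant for those items only, within a set window after receipt. If abstinence is reported, the CO invitation follows.
2. **Sections 7.4 and 7.5.** State that an answer obtained this way counts as the survey report, as it would for a booklet completed by telephone.
3. **Section 20.** Say whether incomplete pages include questionnaire pages, so that staff at all sites apply one rule.

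The cost is a wording change and a small number of short calls by staff who already help participants complete booklets by telephone and telephone them to arrange CO visits. Section 15.2 already provides for the same kind of contact after a reported admission. A participant may disclose allocation during a call. Section 8.8 already accepts that risk for the CO appointment, and keeping the call to the smoking items limits it.
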